## Variables

### Outcomes and endpoints

1. The primary outcome is revision due to prosthetic joint infection (PJI) within 2 years following TKA
2. The first secondary outcome is types of microbial profiles detected in the PJs, short term ( $\leq 90$  days) and long-term (91 days to 2 years)
3. Another secondary outcome is revision due to all causes within 2 years following TKA.

For the revision due to PJI, we will stratify the outcome looking into the proportions of the following groups of bacteria within the first 90 days and between 91 and 730 days following TKA:

- A. PJI due to *Staphylococcus aureus*.
- B. PJI due to Coagulase-negative staphylococci.
- C. PJI due to other gram-positive bacteria.
- D. PJI due to gram-negative bacteria.
- E. PJI due to anaerobic bacteria.
- F. PJI due to mycoplasmic infection.
- G. PJI due to polymicrobial infection.
- H. PJI with negative culture.

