## Definitions

**PJI:** our definition of PJI is adapted from The European Bone and Joint Infection Society (EBJIS) criteria as at least one of the following:

- A. DKR-registered revision surgery due to infection.
- B. At least 2 deep-tissue samples of phenotypically indistinguishable bacteria isolated from at least 3 deep-tissue samples
- C. One or more positive intraoperative samples from a closed fluid aspirate AND a biopsy (fluid AND tissue) of phenotypically indistinguishable bacteria isolated.

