| All cause revision, no. (%) | xx (xx) | xx (xx)   | xx [xx to xx] |
| Adjusted analyses:   |         |           |               |
| N                           | xx      | xx        |               |
| PJI, no. (%)                | xx (xx) | xx (xx)   | xx [xx to xx] |
| All cause revision, no. (%) | xx (xx) | xx (xx)   | xx [xx to xx] |

\*CI: Confidence Interval

**Table 3 (Mockup):** Microbial profiles in revisions for prosthetic joint infection (PJI) within the first 90 days and between 90 days and 2 years postoperatively.

|   | Obese   | Non-Obese | Absolute Risk Difference [95% CI*] |
|---|---------|-----------|------------------------------------|
| N                                  | xx      | xx        |                                    |
| PJI, 90 days, no. (%)              | xx (xx) | xx (xx)   | xx [xx to xx]                      |
| Staphylococcus aureus, no. (%)            | xx (xx) | xx (xx)   | xx [xx to xx]                      |
| Coagulase-negative staphylococci, no. (%) | xx (xx) | xx (xx)   | xx [xx to xx]                      |
| Other gram-positive, no. (%)              | xx (xx) | xx (xx)   | xx [xx to xx]                      |
| Gram-negative, no. (%)                    | xx (xx) | xx (xx)   | xx [xx to xx]                      |
| Anaerobes, no. (%)                        | xx (xx) | xx (xx)   | xx [xx to xx]                      |
| Fungal, no. (%)                           | xx (xx) | xx (xx)   | xx [xx to xx]                      |
| Mycoplasma, no. (%)                       | xx (xx) | xx (xx)   | xx [xx to xx]                      |
| polymicrobial, no. (%)                    | xx (xx) | xx (xx)   | xx [xx to xx]                      |
| Culture-negative, no. (%)                 | xx (xx) | xx (xx)   | xx [xx to xx]                      |
| PJ, 91 days - 2 years, no. (%)     | xx (xx) | xx (xx)   | xx [xx to xx]                      |
| Staphylococcus aureus, no. (%)            | xx (xx) | xx (xx)   | xx [xx to xx]                      |
| Coagulase-negative staphylococci, no. (%) | xx (xx) | xx (xx)   | xx [xx to xx]                      |
| Other gram-positive, no. (%)              | xx (xx) | xx (xx)   | xx [xx to xx]                      |
| Gram-negative, no. (%)                    | xx (xx) | xx (xx)   | xx [xx to xx]                      |
| Anaerobes, no. (%)                        | xx (xx) | xx (xx)   | xx [xx to xx]                      |

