## Sensitivity analyses

A sensitivity analysis will also be done to report PJI-likely revisions and the microbial profiles in these patients. PJI-likely revisions will be defined as revisions surgeries with at least one of the following: A) One single intraoperatively obtained positive culture obtained from the revision surgery (aspiration fluid OR tissue biopsy) regardless of the microorganism. B) One single positive culture obtained from aspiration of synovial fluid regardless of microorganism. If we do not find a difference between obese and non-obese, we will run a sensitivity analysis where we compare morbidly obese patients ( $BMI \geq 40 \text{ kg/m}^2$ ) with other patients ( $BMI < 40 \text{ kg/m}^2$ ). If the primary analysis showed a difference between obese and non-obese, a sensitivity analysis comparing morbidly obese ( $BMI \geq 40 \text{ kg/m}^2$ ) with non-morbidly obese ( $BMI 30-40 \text{ kg/m}^2$ ) will be done.

**Sensitivity analysis table 1:** Incidence for Periprosthetic joint infection-likely (PJI) revision at 2 years in obese and non-obese patients with the relative risk (RR) and an unadjusted and adjusted analyses of the Hazard Ratios (HR) between the 2 groups

|                           | Obese   | Non-Obese | HR [95% CI*]  |
|---------------------------|---------|-----------|---------------|
| Crude analyses:    |         |           |               |
| N                         | xx      | xx        |               |
| PJI-likely, no. (%)       | xx (xx) | xx (xx)   | xx [xx to xx] |
| Adjusted analyses: |         |           |               |
| N                         | xx      | xx        |               |
| PJI-likely, no. (%)       | xx (xx) | xx (xx)   | xx [xx to xx] |

\*CI: Confidence Interval

**Sensitivity analysis table 2:** Prosthetic joint infection-likely (PJI-likely) within the first 90 days and in 91 days-2 years postoperatively stratified by the type of infection

|   | Obese   | Non-Obese | Absolute Risk difference [95% CI*] |
|---|---------|-----------|------------------------------------|
| N   | xx      | xx        |                                    |
| PJI-likely, 90 days, no. (%)           | xx (xx) | xx (xx)   | xx [xx to xx]                      |
| Staphylococcus aureus, no. (%)                | xx (xx) | xx (xx)   | xx [xx to xx]                      |
| Coagulase-negative staphylococci, no. (%)     | xx (xx) | xx (xx)   | xx [xx to xx]                      |

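### As written, the PJI-likely outcome neither contains the primary PJI outcome nor is separate from it, so a shift in its hazard ratio mixes lost confirmed events with added doubtful ones

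*Combined protocol and SAP*

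**What the plan says.** Under Outcomes and endpoints, "The primary outcome is revision due to prosthetic joint infection (PJI) within 2 years following TKA". The groups that follow include "PJI with negative culture", and mock-up Table 3 has a culture-negative row in both time windows.

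Under Definitions, any one of three criteria makes a PJI:

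- Criterion A is "DKR-registered revision surgery due to infection". No culture result is required.
- Criterion B rests on tissue alone: "At least 2 deep-tissue samples of phenotypically indistinguishable bacteria isolated from at least 3 deep-tissue samples". It therefore needs two or more positives.
- Criterion C combines fluid and tissue: "One or more positive intraoperative samples from a closed fluid aspirate AND a biopsy", and the organism must match in both.

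Under Sensitivity analyses, "PJI-likely revisions will be defined as revisions surgeries with at least one of the following". Two routes are then listed. The first is "One single intraoperatively obtained positive culture obtained from the revision surgery", and it may be fluid or tissue with any organism. The second is a single positive culture of aspirated synovial fluid. The section does not say whether *one single* means exactly one or at least one. It does not say whether confirmed PJI is carried into PJI-likely or kept out. Sensitivity table 1 then plans crude and adjusted hazard ratios for PJI-likely on its own.

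**The concern.** A sensitivity analysis with a looser case definition is easiest to read when it keeps every confirmed case and adds the doubtful ones. Any change in the hazard ratio (HR) can then be put down to the additions. A lower-certainty tier kept strictly apart from confirmed cases is also readable. The written PJI-likely outcome is neither: it drops some confirmed cases, keeps others and adds new ones.

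If the PJI-likely HR differs from the primary HR, the reader would not know from the HRs whether doubtful cases diluted the association or confirmed cases went missing. If the two agree, opposite shifts could have cancelled. The undefined *one single* adds a second problem: two analysts could build quite different event sets from the same text.

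**Working it through.** The plan gives no event count or sample size here, so there is no figure to reproduce. The first question is whether every primary PJI is also PJI-likely.

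**Step 1. Compare the definitions case by case.** All cases are revisions. Intraoperative fluid is counted under the intraoperative route, and the aspirate route is taken as a separately obtained sample.

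| Findings | Primary PJI | At least one | Exactly one, per route | Exactly one in total |
|---|---|---|---|---|
| Register-coded, no positive culture | Yes (A) | No | No | No |
| Register-coded, one positive intraoperative culture only | Yes (A) | Yes | Yes | Yes |
| 2 concordant of 3 tissue samples, nothing else | Yes (B) | Yes | No | No |
| 2 concordant of 3 tissue samples, plus one separate aspirate | Yes (B) | Yes | Yes, by aspirate | No |
| Intraoperative fluid and one tissue sample positive | Yes (C) | Yes | No | No |
| Not register-coded, one positive culture | No | Yes | Yes | Yes |

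The last three columns are readings of *one single*. Row 1 is lost under all of them. Row 2 meets both definitions under all of them, so the outcomes are never disjoint. Row 6 is the added, less certain case.

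**Step 2. Enumerate.** Take a register flag (yes/no), 0 to 5 tissue samples with any number positive (21 combinations, same organism), intraoperative fluid positive or not, and separate aspirate positive or not. That gives 2 × 21 × 2 × 2 = 168 patterns. Primary PJI holds in 132: 84 with the register flag (21 × 4) and 48 without it (36 by criterion B, and 12 more by C alone).

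- At least one: 126 of 132 are PJI-likely. The 6 lost are register-coded with no positive culture (0 to 5 tissue samples, all negative). All B and C cases are kept.
- Exactly one, per route: 77 kept, 55 lost.
- Exactly one in total: 17 kept, 115 lost, including every B and C case, since each needs at least two positives.

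These count result patterns, not patients. They show that no reading gives a superset; they do not show how many patients are affected.

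**Step 3. Illustrate the ambiguity, with assumed inputs.** For rare events a composite HR is roughly Σ(aᵢ × HRᵢ) / Σaᵢ, where aᵢ is each component's share of baseline events. Use the at-least-one reading. Set the primary total to 1, with a culture-negative share of 0.05 to 0.30 and added single-positive revisions of 0.2 to 0.5.

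- *Scenario 1:* HR 2.5 for culture-negative cases and 1.3 for all others. The primary HR is 1.36 to 1.66, PJI-likely is 1.30 throughout, and the union of the two outcomes is 1.34 to 1.60.
- *Scenario 2:* HR 1.5 for all primary cases and 1.0 for added ones. The primary HR is 1.50, PJI-likely is 1.29 to 1.41, and the union is 1.33 to 1.42.

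At a culture-negative share of 0.20 and additions of 0.5:

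- Scenario 1, primary: 0.8 × 1.3 + 0.2 × 2.5 = 1.54. PJI-likely: (0.8 × 1.3 + 0.5 × 1.3) / 1.3 = 1.30. Union: (1.54 + 0.5 × 1.3) / 1.5 = 1.46.
- Scenario 2, primary: 1.50. PJI-likely: (0.8 × 1.5 + 0.5 × 1.0) / 1.3 = 1.31. Union: (1.5 + 0.5) / 1.5 = 1.33.

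The planned pair of HRs is nearly the same (1.54 and 1.30; 1.50 and 1.31), although the fall comes from removal in the first scenario and mainly from dilution in the second. None of these component HRs or shares comes from the documents.

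**The case against.** The section says the analysis is meant to report PJI-likely revisions and their microbial profile. It never promises a nested robustness test, and a sensitivity outcome need not be nested. PJI-likely may be intended as a separate, lower-certainty tier. This is fair as far as intent goes, but the written rule does not produce that tier either, because register-coded cases with one positive culture fall into both outcomes.

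On the at-least-one reading, part of the loss is visible. Table 3 gives culture-negative counts by BMI group and window, so the added cases are roughly PJI-likely minus (PJI minus culture-negative). This stands for crude counts. It yields no HR for either component, and it fails if *one single* means exactly one, because lost cases with several positive cultures have no line in any table.

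If culture-negative and culture-positive infections have similar HRs, the removal matters little. In scenario 2, PJI-likely and the union differ by at most 0.04 (1.29 against 1.33). That also stands.

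Some stronger readings are tempting but not supported:

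- A reader might take the missing culture-negative row in sensitivity table 2 as proof of the exclusion. Sensitivity table 4 reports PJI itself and lacks the row too, so the tables prove nothing; the definitions carry the point.
- A reader might infer that every criterion B case drops out on the literal wording. That holds only if *one single* means one positive in total; applied per route, some return through the aspirate.
- A reader might conclude that the analysis says nothing about robustness. A changed HR would still show dependence on the outcome definition, but would not by itself say why.

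**Conclusion.** The point holds on the text. Under every reading of *one single*, the PJI-likely outcome omits some primary PJI events, and it is not disjoint from the primary outcome. On the most generous reading the loss is confined to register-coded revisions for infection without a positive culture. On the stricter readings it extends to many confirmed infections with several positive cultures, or to all criterion B and C cases.

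The size cannot be derived from the documents. They give an expected 2-year incidence of about 1%, but neither the cohort size nor the culture-negative share. Purely as an assumption, 40,000 arthroplasties would give 0.01 × 40,000 = 400 events, and a culture-negative share of 5 to 20% would mean 20 to 80 of them lost on the at-least-one reading. The HR shifts shown rest on further assumptions and illustrate the mechanism only.

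The primary estimate is unaffected. What suffers is the interpretation of a supplementary analysis. The change is worth making before the data are analysed because it is specific and nearly free.

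**What to change.** 1. Replace *one single* with *at least one* in both PJI-likely routes.
2. Run the sensitivity HR, crude and adjusted, on the union of primary PJI (A, B or C) and PJI-likely. Suggested wording:

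> The sensitivity outcome is a first revision within 730 days that meets primary PJI criterion A, B or C, or that has at least one positive culture from an intraoperative sample or a synovial aspirate.

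3. Report revisions that are PJI-likely but not PJI on a separate line, by BMI group and time window.
4. Add a culture-negative row to the union table.

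This serves both purposes: the union keeps every primary event, and the separate line shows the lower-certainty tier on its own. The cost is some SAP wording and a few table rows, with no new data. The union outcome will be less specific than the primary one, and the separate line shows how many events that concerns.

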## Statistical Methods

We will use descriptive statistics to summarize baseline characteristics of the two groups and will compare them using standardized differences. The 2-year (730 days) cumulative incidence of PJI will be reported for both groups. Hazard ratios with corresponding two-sided 95% confidence intervals (CIs) will be estimated using a Cox proportional hazards regression model. We will fit both unadjusted (crude) models and propensity adjusted models using inverse probability of treatment weighting (IPTW). For the adjusted model, propensity scores will be calculated based on age in years, female sex, completed education, household income, comedications, and ECM (all collected prior to surgery). Subsequent stratified analyses will categorize the observed PJI cases by bacterial infection type (within the first 90 days postoperatively or between 91 days and 2 years) and compare crude proportions between groups based on the absolute risk difference with 95% confidence intervals.

[figure not shown]
We present several analyses corresponding to the main results with 95% confidence intervals rather than P values, and comply with 2 Acta Orthopaedica principles for concluding whether scientifically important differences exist:

- A statistically non-significant test is not sufficient to claim "no difference." To show "no difference," a smallest clinically relevant size of the difference (it might be 0) must be defined. If all clinically relevant differences are excluded from the difference's confidence interval, a "no difference" or similarity/comparability conclusion is reasonable.
- A statistically significant test does not necessarily imply a clinically important difference. The importance of the tested null hypothesis depends on the smallest clinically relevant difference that should be defined a priori. If the difference's confidence interval excludes all clinically irrelevant differences, a conclusion concerning the existence of a clinically important difference is reasonable.

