To evaluate imprecision in the estimated treatment effect, a clinically important difference must first be defined. Based on an expected 2-year incidence of PJI of about 1%, a 50% increase in risk would be considered clinically relevant. In a time-to-event analysis, this corresponds to a hazard ratio of 1.5. Accordingly, non-inferiority—or absence of a clinically meaningful increase in risk—will be established if the upper bound of the 95% confidence interval for the hazard ratio remains below 1.5. We will visualize the 2-year cumulative incidence of all outcomes for both groups using the cumulative incidence functions (CIFs).

**Handling of missing data and sensitivity analyses:** Missing data is unavoidable in epidemiological and clinical research and must be explained otherwise it could undermine the credibility and validity of the research results. Missing values, for either predictors or outcomes, occur in all types of medical research. Unless prompted to do otherwise, most statistical packages explicitly exclude individuals with any missing value on any of the data analyzed. The resulting so-called "available case" or "complete case" analysis is the most common "default approach" to handle missing data, although it is rarely justified. Subjects with missing weight or height will be excluded from the analysis. Missingness of data on some of the covariates used for adjusting will be ignored but the subjects will not be excluded. Patients who will be lost during the follow up period (e.g., due to death or migration) are expected to be extremely few and no systematic difference is expected to be seen.

Therefore, this missingness of outcome data will be assumed "Missing completely at random" (MCAR), as there is no evidence to suggest systematic differences between the missing values and the observed values and will be ignored. For the purpose of sensitivity, we will potentially re-do the main analysis where missing outcome data is replaced twice, using best-case imputation ( $y=0$ ; no PJI) and worst-case imputation ( $y=1$ , PJI yes).

[figure not shown]
**Figure 1 (Mockup):** study flow chart

**Table 1 (Mockup).** Baseline characteristics at time of total knee arthroplasty

|  | Obese | Non-Obese | Std. Diff |
|--|-------|-----------|-----------|
| Age, years                                 |       |           |           |
| Female Sex, no. (%)                        |       |           |           |

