| Other gram-positive, no. (%)                  | xx (xx) | xx (xx)   | xx [xx to xx]                      |
| Gram-negative, no. (%)                        | xx (xx) | xx (xx)   | xx [xx to xx]                      |
| Anaerobes, no. (%)                            | xx (xx) | xx (xx)   | xx [xx to xx]                      |
| Fungal, no. (%)                               | xx (xx) | xx (xx)   | xx [xx to xx]                      |
| Mycoplasma, no. (%)                           | xx (xx) | xx (xx)   | xx [xx to xx]                      |
| Multibacterial, no. (%)                       | xx (xx) | xx (xx)   | xx [xx to xx]                      |
| PJI-likely, 91 days - 2 years, no. (%) | xx (xx) | xx (xx)   | xx [xx to xx]                      |
| Staphylococcus aureus, no. (%)                | xx (xx) | xx (xx)   | xx [xx to xx]                      |
| Coagulase-negative staphylococci, no. (%)     | xx (xx) | xx (xx)   | xx [xx to xx]                      |
| Other gram-positive, no. (%)                  | xx (xx) | xx (xx)   | xx [xx to xx]                      |
| Gram-negative, no. (%)                        | xx (xx) | xx (xx)   | xx [xx to xx]                      |
| Anaerobes, no. (%)                            | xx (xx) | xx (xx)   | xx [xx to xx]                      |
| Fungal, no. (%)                               | xx (xx) | xx (xx)   | xx [xx to xx]                      |
| Mycoplasma, no. (%)                           | xx (xx) | xx (xx)   | xx [xx to xx]                      |
| Multibacterial, no. (%)                       | xx (xx) | xx (xx)   | xx [xx to xx]                      |

\*The 95% confidence intervals (CI) will not be adjusted for multiplicity and should not be used in place of hypothesis testing.

**Sensitivity analysis table 3:** Incidence for Periprosthetic joint infection (PJI) and all cause revision at 2 years in morbidly obese and non-morbid patients with an unadjusted and adjusted analyses of the Hazard Ratios (HR) between the 2 groups

|                                     | Morbidly-Obese | Non-morbid | HR [95% CI*]  |
|-------------------------------------|----------------|------------|---------------|
| Crude analyses:              |                |            |               |
| N                                   | xx             | xx         |               |
| PJI, no. (%)                        | xx (xx)        | xx (xx)    | xx [xx to xx] |

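### The primary result selects the comparator for BMI ≥40 by an undefined test of difference; report both named contrasts in sensitivity table 3 whatever that result is (low severity)

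*Combined protocol and SAP*

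**What the plan says.** The Sensitivity analyses section of the combined protocol and SAP sets two conditions. The first reads "If we do not find a difference between obese and non-obese, we will run a sensitivity analysis where we compare morbidly obese patients", with all patients below BMI 40 as comparator. The second reads "If the primary analysis showed a difference between obese and non-obese, a sensitivity analysis comparing morbidly obese", with BMI 30-40 as comparator. Only the second condition names the primary analysis; I take both to refer to it.

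Sensitivity tables 3 and 4 have one comparator column, labelled Non-morbid in either case. The title of table 3 covers "all cause revision at 2 years in morbidly obese and non-morbid patients".

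The Statistical Methods section fits a crude and an IPTW Cox model and does not say which is decisive. Results are to be presented "with 95% confidence intervals rather than P values". It contains these rules about differences:

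- The first principle is that non-significance alone does not show no difference. Such a conclusion is reasonable if the CI excludes every clinically relevant difference.
- The second principle is that, if the "confidence interval excludes all clinically irrelevant differences, a conclusion concerning the existence of a clinically important difference is reasonable".
- For the margin, "a 50% increase in risk would be considered clinically relevant", expressed as a hazard ratio of 1.5. Absence of a meaningful increase "will be established if the upper bound of the 95% confidence interval for the hazard ratio remains below 1.5".

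The Sensitivity analyses section refers to none of these rules.

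**The concern.** A rule that picks an analysis from a result protects against choice after the fact only if each result leads to one analysis. This rule turns on the word 'difference', with no model and no criterion attached. Two analysts with the same primary output could both follow the plan and still fill sensitivity table 3 with hazard ratios against different comparators.

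Even with a clear trigger, the quantity reported for BMI ≥40 would depend on the primary result, and only one of two clinically distinct contrasts would appear. The adjusted hazard ratios for the other, for PJI and for all-cause revision, would be lost. Since the comparator column has the same label in both cases, a reader would have to infer the comparator from the N row.

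**Working it through.** **1. The plan's own figure.** A 50% increase on a 2-year incidence of about 1% gives 1.5%. As a hazard ratio this is ln(1 − 0.015) / ln(1 − 0.010) = 1.504, which agrees with the stated 1.5.

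**2. Can one CI go to both branches?** The documents give no N, event count or obesity share, so I assume 600 PJI events, 40% obese and an estimated HR of 1.25.

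- SE(log HR) = 1/√(600 × 0.4 × 0.6) = 0.0833.
- 95% CI = 1.25 × exp(±1.96 × 0.0833) = 1.06 to 1.47.

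The interval excludes 1, so in the ordinary sense a difference has been found. Its upper bound is also below 1.5, so the margin rule and the first principle allow a conclusion of no difference. The Sensitivity analyses section does not say which applies. Any CI lying wholly between 1.0 and 1.5 has this property.

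How often this happens depends entirely on assumptions. With 40% obese, 1% risk in the non-obese and a normal approximation, a true HR of 1.2 gives such a CI in 0%, 8% and 42% of studies at N = 20,000, 40,000 and 60,000. At a true HR of 1.8 it essentially never occurs. These figures are illustrative only.

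**3. Can the model decide?** Assume N = 40,000, BMI shares of 56% (<30), 40% (30 to <40) and 4% (≥40), 1% risk at BMI <30, and class HRs of 1, 1.2 and 2.0.

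- Events: 22,400 × 0.010 = 224; 16,000 × 0.012 = 192; 1,600 × 0.020 = 32. The obese group has 192 + 32 = 224.
- Primary crude HR = (40 × 1.2 + 4 × 2.0)/44 = 1.27.
- SE = √(1/224 + 1/224) = 0.094, giving a CI of 1.06 to 1.53.
- An IPTW HR of 1.20 with the same SE would have a CI of 0.997 to 1.44.

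Under an exclude-1 criterion the crude model finds a difference and the IPTW model does not. The 1.20 was chosen to show that this can happen, not how likely it is.

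**4. Do the two contrasts differ?** With rare events, each HR is the class HR at BMI ≥40 divided by the share-weighted mean of the comparator. The shares are as in step 3.

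| Assumed class HRs (<30 / 30 to <40 / ≥40) | ≥40 vs <40 | ≥40 vs 30 to <40 |
|---|---|---|
| 1 / 1.2 / 2.0 | 2.0 / [(56 × 1 + 40 × 1.2)/96] = 2.0/1.083 = 1.85 | 2.0/1.2 = 1.67 |
| 1 / 1.5 / 2.5 | 2.5 / [(56 × 1 + 40 × 1.5)/96] = 2.5/1.208 = 2.07 | 2.5/1.5 = 1.67 |
| 1 / 1 / 2.0 | 2.00 | 2.00 |

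The contrasts coincide when BMI 30 to <40 carries the same risk as BMI <30, as in the third row.

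**5. The gap against sampling error.** For the first row at N = 40,000:

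- ≥40 vs <40: SE = √(1/32 + 1/416) = 0.183, CI 1.29 to 2.64.
- ≥40 vs 30 to <40: SE = √(1/32 + 1/192) = 0.191, CI 1.15 to 2.42.

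The intervals overlap almost entirely.

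**6. What can be recovered.** Subtracting the BMI ≥40 counts from the obese counts in main Table 2 gives 30 to <40. Adding 30 to <40 to the non-obese counts gives <40. Crude numbers for the untaken contrast therefore follow by arithmetic, and the organism counts of table 4 follow in the same way from main Table 3. An IPTW hazard ratio does not, because it needs its own propensity model and weights.

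**The case against.** The strongest case for the plan is that this is a reasonable staged design. Both contrasts are written down in advance and, under any single definition of a difference, the two conditions cover every possible result. If BMI 30 makes no difference, pooling everyone below 40 is coherent; if it does, comparing within the obese is the natural next question. One sentence naming the model and the criterion would remove the ambiguity. When obesity does matter, ≥40 vs <40 averages over unequal risks and is harder to interpret. The footnote to sensitivity table 4 also warns against using its intervals in place of hypothesis tests.

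Most of this stands, and it keeps the severity low. Defining the trigger would cure the ambiguity, but it would still leave the reported quantity dependent on the primary result and the other adjusted hazard ratios unavailable. The interpretive problem with ≥40 vs <40 is eased when the within-obese contrast stands beside it.

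A reader might also infer that most studies would be sent to conflicting branches. That needs one of two further definitions. One requires the lower limit to exceed 1.5, but the second principle concerns a clinically important difference, whereas the Sensitivity analyses section speaks only of a difference; this definition is arguable but less natural. The other treats an upper limit of 1.5 or more as a difference found. That is a converse which the plan never states. A CI covering both 1 and 1.5 is most simply read as a difference not found. I place no weight on conflict rates built on either definition.

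**Conclusion.** The point holds at low severity. The comparator for BMI ≥40 depends on the primary result, and the plan states neither the model nor the CI criterion that defines a difference. The existence of a conflict follows from the text: a CI inside 1.0 to 1.5 excludes 1 and also satisfies the plan's rule for no meaningful increase.

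The numerical size rests on assumed N, BMI shares and class HRs. In the first example the branches estimate 1.85 and 1.67, a gap that is small next to sampling error; with equal risk below BMI 40 the choice does not change the quantity estimated. The certain loss is the adjusted hazard ratios for PJI and all-cause revision in the contrast not reported.

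A reader might go further and infer that the rule is improvised or that it compromises the main findings. The documents do not support this: the branching is pre-specified, and the primary hazard ratio and main Tables 2 and 3 do not depend on it.

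Two smaller matters belong with the point: the Non-morbid label does not identify the comparator, and 30-40 overlaps with ≥40 at exactly 40.

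**What to change.** - Delete both conditions in the Sensitivity analyses section. Whatever the primary result, report both contrasts already named there: BMI ≥40 vs <40, and BMI ≥40 vs 30 to <40.
- In sensitivity table 3, give both contrasts for PJI and all-cause revision, crude and IPTW, with a propensity model fitted separately for each contrast.
- In sensitivity tables 3 and 4, replace the Non-morbid label with the actual comparator, and write 30 to <40 throughout.
- A second contrast in sensitivity table 4 is optional. Its crude counts can be derived from other tables, and events are few. In the assumed example, BMI ≥40 has 16 to 48 PJI events for N = 20,000 to 60,000, or on average 1 to 3 for each of the 16 organism-by-window rows.

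The cost is a change of SAP wording, one more propensity model and extra columns, all on data already held. The intervals for BMI ≥40 will be wide, and the text should say so. No new contrast is introduced and no primary analysis changes.
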